5.3.3.2. Exposure

No imputation will be done for first dose date. Date of last dose of study intervention, if unknown or partially unknown, will be imputed as follows:

- If the last date of study intervention is completely missing and there is no End of Treatment (EOT) CRF page and no death date, the participant should be considered to be ongoing and use the data cutoff date for the analysis as the last dosing date; or

- If the last date of study intervention is completely or partially missing and there is either an EOT CRF page or a death date available (on or prior to the data cutoff date), then impute this date as the last dose date:
 - = 31DECYYYY, if only Year is available and Year < Year of min (EOT date, death date);
 - = Last day of the month, if both Year and Month are available and Year = Year of min (EOT date, death date) and Month < the month of min (EOT date, death date); or
 - = min (EOT date, death date), for all other cases.

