MMM < Month of min [max(PD date + 1 day, last dose of study intervention + 1 day), end date of new anticancer therapy];
THEN imputed start date = DAY (Last day of MMM) MMM YYYY;
 - ELSE IF YYYY = Year of min [max(PD date + 1, last dose of study intervention + 1), end date of new anticancer therapy], AND
MMM = Month of min [max(PD date + 1 day, last dose of study intervention + 1 day), end date of new anticancer therapy];

THEN imputed start date = min [max(PD date + 1 day, last dose of study intervention + 1 day), end date of new anticancer therapy];

- ELSE IF YYYY = Year of min [max(PD date + 1, last dose of study intervention + 1), end date of new anticancer therapy], AND

MMM > Month of min [max(PD date + 1 day, last dose of study intervention + 1 day), end date of new anticancer therapy];

THEN imputed start date = 01 MMM YYYY;

- ELSE IF YYYY < Year of min [max(PD date + 1, last dose of study intervention + 1), end date of new anticancer therapy],

THEN imputed start date = DAY (Last day of MMM) MMM YYYY;

- ELSE IF YYYY > Year of min [max(PD date + 1, last dose of study intervention + 1), end date of new anticancer therapy],

THEN imputed start date = 01 MMM YYYY.

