5.3.3.5. Other Dates

Imputation methods for other partial dates are as follows:

- If the day of the month is missing for a start date used in a calculation, the first day of the month will be used to replace the missing date;
- If both the day and month are missing, the first day of the year is used;
- For stop dates, the last day of the month, or last day of the year is used if the day or day and month are missing, respectively;
- If the date is completely missing, no imputation will be performed.

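### SAP 5.3.3.2 has no branch for a last-dose date with a known month in an earlier calendar year, so the catch-all imputes an EOT or death date that the recorded month rules out

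*SAP*

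**What the plan says.** The rule in SAP 5.3.3.2 (Exposure) covers this situation: "If the last date of study intervention is completely or partially missing and there is either an EOT CRF page or a death date available". Call the earlier of the EOT and death dates the reference date. There are three branches.

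- First: "31DECYYYY, if only Year is available and Year < Year of min (EOT date, death date").
- Second: the date becomes the end of the recorded month, but only "if both Year and Month are available and Year = Year of min (EOT date, death date"). The recorded month must also precede the month of the reference date.
- Third: "min (EOT date, death date), for all other cases".

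SAP 5.3.3.4, which imputes the start of new anticancer therapy, has a further branch when year and month are known: "ELSE IF YYYY < Year of min [max(PD date + 1, last dose of study intervention + 1), end date of new anticancer therapy"], followed by "THEN imputed start date = DAY (Last day of MMM) MMM YYYY".

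SAP 5.3.3.5 has a general rule: "For stop dates, the last day of the month, or last day of the year is used" when the day, or the day and month, are missing. That section is limited to dates not covered elsewhere, so it does not override the specific last-dose rule.

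**The concern.** A recorded year and month in a calendar year before the reference year satisfies neither of the first two branches. The first requires that only the year be known; the second requires equal years. The third branch then gives an explicit instruction to use the reference date, which cannot lie in the recorded month. Because the text is explicit, a program that follows it will reproduce the error, and a second programmer working from the same text will agree.

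The last-dose date matters in several places:

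- treatment duration (SAP 6.7.3);
- the on-treatment period, which runs to 90 days after last dose or the day before new anticancer therapy, whichever is earlier, and so decides which adverse events are treatment-emergent (SAP 3.5 and 3.5.1);
- deaths within 90 days of last dose (SAP 6.8.2);
- the imputed start of new anticancer therapy, when that date is also incomplete (SAP 5.3.3.4).

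**Working it through.** The plan gives no figure to reproduce, so the check is to apply the three branches to dates. All dates below are illustrative assumptions.

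**Step 1. Apply the rule as written.** Excess is the number of days from the last day that the record allows to the imputed date.

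| Recorded last dose | Reference date | Branch reached | Imputed date | Last day allowed | Excess (days) |
|---|---|---|---|---|---|
| 2022 only | 10 Jan 2023 | first | 31 Dec 2022 | 31 Dec 2022 | 0 |
| Dec 2022 | 10 Jan 2023 | third | 10 Jan 2023 | 31 Dec 2022 | 10 |
| Dec 2022 | 14 Jan 2023 | third | 14 Jan 2023 | 31 Dec 2022 | 14 |
| Nov 2022 | 20 Jan 2023 | third | 20 Jan 2023 | 30 Nov 2022 | 31 + 20 = 51 |
| Oct 2022 | 3 Feb 2023 | third | 3 Feb 2023 | 31 Oct 2022 | 30 + 31 + 31 + 3 = 95 |
| Jan 2023 | 15 Mar 2023 | second | 31 Jan 2023 | 31 Jan 2023 | 0 |
| Jan 2023 | 10 Jan 2023 | third | 10 Jan 2023 | 10 Jan 2023 | 0 |

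Rows 1 and 2 show the inconsistency inside the section: knowing the month as well as the year makes the imputed date worse. The last two rows show that same-year cases work.

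**Step 2. Check that this is general.** Take every recorded month from January 2021 up to the month of the reference date, with reference dates on days 1, 15 and 28 of each month in 2022 to 2024. The number of combinations is 3 × [12 × (12 + 24 + 36) + 3 × 78] = 3 × 1,098 = 3,294. Of these, 3 × 12 × 72 = 2,592 have an earlier recorded year. All 2,592 give a date outside the recorded month; none of the other 702 does. With the second branch extended to earlier years, the count falls from 2,592 to 0. These counts show that the error is systematic when the branch is reached; they say nothing about how often that will happen.

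**Step 3. Which errors fit the visit schedule.** The Part 2 schedule of assessments puts the EOT visit 14 days after the final dose. The Part 1 header is not consistently legible, and I assume the same. With a 14-day gap, only last doses from 18 December (18 December + 14 days = 1 January) to 31 December (EOT 14 January) cross the year end, so the excess over 31 December is 1 to 14 days. The 51- and 95-day rows need a later EOT, for example after a dose hold (Protocol 6.5.1.2 allows 4 weeks, or 8 on Q4W, before permanent discontinuation), or a death date with no earlier EOT date.

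**Step 4. Effect on derived quantities.** Take December 2022 with EOT on 10 January 2023, and assume a first dose on 1 March 2022.

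- Treatment duration = (last dose − first dose + 1)/7. With 31 December 2022: 306/7 = 43.71 weeks. As written: 316/7 = 45.14 weeks.
- Last dose + 90 days moves from 31 March 2023 to 10 April 2023.
- Cumulative dose is the sum of doses actually given, so it does not change.
- Overall dose intensity is cumulative dose divided by intended duration, which uses the last zero or non-zero dose date. If the imputed date enters that denominator, dose intensity falls.

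For the death window, take October 2022 with no EOT date and death on 3 February 2023. Death is at least 95 days after any dose in October, so outside the 90-day window. As written, last dose is set to the day of death, the gap is 0 and the death is counted.

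**The case against.** The strongest reply is that the rule will almost never be reached. Protocol 6.4 has doses given at the site under supervision, with the date and time of each recorded in source and CRF. The defect needs a last-dose record missing only its day and a reference date in a later calendar year, and nothing in the documents shows that even one such participant exists. SAP 5.3 also requires imputed values to be flagged in listings, so an odd date would be visible. This stands, and it keeps the point minor. A flag does not correct the date in the summary tables, however.

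A second reply is that a later last-dose date may be a deliberate, inclusive choice for safety capture, and that SAP 5.3.3.4 concerns a different variable. The mismatch with 5.3.3.4 alone would not prove an error. But a policy of that kind would not give 31 December when only the year is known and a date in January when the month is known too. The year-only and same-year branches both use the latest day that the record allows; the earlier-year case breaks that pattern.

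A reader might also infer that exposure in general is overstated. Only treatment duration is: cumulative dose is unchanged, and dose intensity would fall, if it moved at all.

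**Conclusion.** The rule is wrong as written for one identifiable case: year and month known, year earlier than the reference year. No other section repairs it. The effect is rare and usually small: up to about 14 days past 31 December if EOT follows the last dose by about 14 days, and more only with a delayed EOT or a later death date as reference. Treatment duration is overstated. The on-treatment window can lengthen by the same number of days unless new anticancer therapy starts first, and a death can enter the 90-day table.

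Three stronger readings are not supported.

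- Errors of 51 or 95 days are not typical; they depend on the assumptions in step 3.
- Censoring of PFS and DOR is not generally affected. That route needs the start date of new therapy to be incomplete in the same participant. Even then, the imputed start also depends on the progression date and the end date of the new therapy, and censoring falls at the last adequate assessment before it.
- The primary endpoint, Grade ≥2 CRS in Cycle 1, and its decision rule are not materially affected.

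**What to change.** In SAP 5.3.3.2, extend the condition of the second branch. Assign the last day of the recorded month when year and month are both available and either the year is earlier than the year of the reference date, or the years are equal and the month is earlier. Leave the first and third branches as they are. Year-only, same-year and same-month results do not change, and the section then agrees with SAP 5.3.3.4. The cost is one line of SAP text and one condition in the derivation program, with no change to data collection.

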5.3.3.3. Date of Death

Missing or partial death dates will be imputed based on the last contact date:

- If the date is missing, it will be imputed as the day after the date of last contact;
- If the day or both day and month is missing, death will be imputed to the maximum of the full (non-imputed) day after the date of last contact and the following:
 - Missing day: 1st day of the month and year of death;
 - Missing day and month: January 1st of the year of death.

5.3.3.4. Date of Start of New Anticancer Therapy

Incomplete dates for start date of new anticancer therapy (drug therapy, radiation with curative intent and transplant) will be imputed as follows and will be used for determining censoring dates for efficacy analyses and in the derivation of the end of the on-treatment period. PD date below refers to PD date by investigator assessment. If the imputation results in an end date prior to the imputed start date, then the imputed start date should be set to the end date.

- The end date of new anticancer therapy will be included in the imputations for start date of new anticancer therapy. If the end date of new anticancer therapy is
 - completely missing then it will be ignored in the imputations below;
 - partially missing with only year (YYYY) available then the imputations below will consider 31DECYYYY as the end date of the new anticancer therapy;
 - partially missing with only month and year available then the imputations below will consider the last day of the month for MMMYYYY as the end date of the new anticancer therapy.

- For participants who have not discontinued study intervention at the analysis cutoff date, last dose of study intervention is set to the analysis cutoff date in the imputations below.
- If the start date of new anticancer therapy is completely or partially missing, then the imputed start date of new anticancer therapy is derived as follows:
 - Start date of new anticancer therapy is completely missing
 - Imputed start date = min [max(PD date + 1, last dose of study intervention + 1), end date of new anticancer therapy].
 - Only year (YYYY) for start of anticancer therapy is available:
 - IF YYYY < Year of min [max(PD date + 1, last dose of study intervention + 1), end date of new anticancer therapy];
 - THEN imputed start date = 31DECYYYY;
 - ELSE IF YYYY = Year of min [max(PD date + 1, last dose of study intervention + 1), end date of new anticancer therapy];
 - THEN imputed start date = min [max(PD date + 1, last dose of study intervention + 1), end date of new anticancer therapy];
 - ELSE IF YYYY > Year of min [max(PD date + 1, last dose of study intervention + 1), end date of new anticancer therapy];
 - THEN imputed start date = 01JANYYYYY;
 - Both Year (YYYY) and Month (MMM) for start of anticancer therapy are available:
 - IF YYYY = Year of min [max(PD date + 1, last dose of study intervention + 1), end date of new anticancer therapy], AND
MMM < Month of min [max(PD date + 1 day, last dose of study intervention + 1 day), end date of new anticancer therapy];
THEN imputed start date = DAY (Last day of MMM) MMM YYYY;
 - ELSE IF YYYY = Year of min [max(PD date + 1, last dose of study intervention + 1), end date of new anticancer therapy], AND
MMM = Month of min [max(PD date + 1 day, last dose of study intervention + 1 day), end date of new anticancer therapy];

THEN imputed start date = min [max(PD date + 1 day, last dose of study intervention + 1 day), end date of new anticancer therapy];

- ELSE IF YYYY = Year of min [max(PD date + 1, last dose of study intervention + 1), end date of new anticancer therapy], AND

MMM > Month of min [max(PD date + 1 day, last dose of study intervention + 1 day), end date of new anticancer therapy];

THEN imputed start date = 01 MMM YYYY;

- ELSE IF YYYY < Year of min [max(PD date + 1, last dose of study intervention + 1), end date of new anticancer therapy],

THEN imputed start date = DAY (Last day of MMM) MMM YYYY;

- ELSE IF YYYY > Year of min [max(PD date + 1, last dose of study intervention + 1), end date of new anticancer therapy],

THEN imputed start date = 01 MMM YYYY.

5.3.3.5. Other Dates

Imputation methods for other partial dates are as follows:

- If the day of the month is missing for a start date used in a calculation, the first day of the month will be used to replace the missing date;
- If both the day and month are missing, the first day of the year is used;
- For stop dates, the last day of the month, or last day of the year is used if the day or day and month are missing, respectively;
- If the date is completely missing, no imputation will be performed.

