3.5. Safety Endpoints

Safety endpoints will be summarized based on the on-treatment period unless otherwise specified.

The on-treatment period is defined as the time from the first dose of study intervention through the minimum of 90 days after last dose, or (start day of new anticancer therapy - 1 day). Anticancer therapy includes drug therapy and radiation with curative intent; the start of new anticancer therapy after the first dose of study intervention is derived as outlined in [Section 5.2.6](#). Adverse events occurring on the same day as the first dose of study intervention will be considered to have occurred during the on-treatment period. All other assessments which occur on the same day as the first dose of study intervention will be considered baseline assessments (see [Section 3.4](#) for the definition of baseline).

Safety data collected after the on-treatment period as described above will be listed but not summarized.

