3.5.1. Adverse Events

An adverse event (AE) is considered treatment-emergent relative to the study intervention if the event start date is during the on-treatment period (including on the date of first dose).

AEs will be characterized by type, severity, timing, seriousness, and relationship to study intervention.

AEs (except CRS and ICANS) will be graded by the investigator according to the NCI CTCAE version 5.0. CRS and ICANS will be graded according to the ASTCT criteria.¹ All AEs will be coded using the most current version of MedDRA.

TEAEs leading to dose interruption (prior to protocol amendment 2) will be derived from the exposure CRF (dose adjustment reason as adverse event and actual dose taken of 0 for interruption and >0 for reduction) and then linked programmatically to the adverse event CRF by the AE identifier.

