5.2.4. Definition of Study Day

The study day for assessments occurring on or after the first dose of study intervention (eg, adverse event onset, disease measurement) will be calculated as:

$$\text{Study day} = \text{Date of the assessment/event} - \text{start date of study intervention} + 1.$$

The study day for assessments occurring prior to the first dose of study intervention (eg, baseline characteristics, medical history) will be negative and calculated as:

$$\text{Study day} = \text{Date of the assessment/event} - \text{start date of study intervention}.$$

The study day will be displayed in all relevant data listings.

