5.3.3. Handling of Incomplete or Missing Dates

5.3.3.1. Adverse Events

AE Onset Date: If the AE onset date is completely missing, and if the date of first dose is earlier than AE stop date, then the onset date will be assigned as the date of first dose. Otherwise if the date of first dose is after the AE stop date then the AE onset date will be imputed as the earliest of non-missing AE stop date or informed consent date.

AE Stop Date: If the AE stop date is completely missing then the stop date will be imputed as the latest of the participant withdrawal/completion date, death date, last dose of study intervention, or AE onset date.

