6.8.1. Adverse Events

All analyses will be based on treatment emergent adverse events (TEAE) unless otherwise specified. Treatment emergent is defined in [Section 3.5](#). AEs not considered treatment emergent will be flagged in data listings. Summaries of TEAEs due to COVID-19 may be produced if appropriate.

A high-level summary of adverse events (all causality and treatment-related, separately) will include the number and percent of participants with:

- Any TEAEs;
- Serious TEAEs;
- Grade 3-4 TEAEs ;
- Grade 5 TEAEs;
- TEAEs leading to dose interruptions;
- TEAEs leading to dose reductions;
- TEAEs leading to dose interruptions or reductions;
- TEAEs leading to permanent discontinuation of study intervention;
- CRS;
- ICANS;
- Peripheral neuropathy.

Seriousness, toxicity grade, and withdrawal from drug are as reported by the investigator on the adverse event CRF.

An event will be considered treatment related if the investigator considered the event related to the study drug, or if relationship is missing.

For all the AE summaries by SOC and PT, or PT only, the following cytopenias will be clustered. Each participant will be counted only once within each SOC and clustered terms. However, the number of total events will be based on the individual PTs.

- Thrombocytopenia (PT=Thrombocytopenia; Platelet count decreased);
- Anaemia (PT=Anaemia; Haemoglobin decreased, Red blood cell count decreased, Haematocrit decreased, Normochromic anaemia, Normocytic anaemia, Normochromic normocytic anaemia);

- Neutropenia (PT=Neutropenia; Neutrophil count decreased, Neutrophil percentage decreased, Cyclic neutropenia, Agranulocytosis, Granulocytopenia, Granulocyte count decreased);
- Leukopenia (PT=Leukopenia; White blood cell count decreased);
- Lymphopenia (PT=Lymphopenia and PT=Lymphocyte count decreased, Lymphocyte percentage decreased, CD4 lymphocytes decreased, CD4 lymphocyte percentage decreased, CD8 lymphocytes decreased, CD8 lymphocyte percentage decreased).

Summaries by SOC and PT (by alphabetical order for SOC and by descending order of frequency for PT in Part 1 and Part 2 combined) will be provided for:

- Any TEAEs (all causality and treatment-related);
- TEAEs by maximum toxicity grade (all causality and treatment-related);
- TEAEs with Grade 3-4 (all causality and treatment-related);
- TEAEs leading to death (all causality and treatment-related);
- TEAEs leading to dose interruptions (all causality);

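### An AE onset with only the day missing is set to the first of the month, so events after dosing in the month of first dose are dated before treatment and leave the TEAE tables

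*SAP*

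**What the plan says.** SAP section 5.3.3.1 gives one rule for AE onset, and it covers only a wholly absent date: "If the AE onset date is completely missing, and if the date of first dose is earlier than AE stop date", the onset becomes the date of first dose. If the event stopped before first dose, the onset is placed before treatment. The section does not mention an onset with a known month or year.

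SAP section 5.3.3.5 then collects what is left: "Imputation methods for other partial dates are as follows". For start dates it says "If the day of the month is missing for a start date used in a calculation, the first day of the month will be used", and "If both the day and month are missing, the first day of the year is used". It contains no comparison with first dose.

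Three other places decide what the imputed date does:
- Section 3.5: "The on-treatment period is defined as the time from the first dose of study intervention through the minimum of 90 days after last dose", or the day before new anticancer therapy if that comes first.
- Section 3.5.1: "An adverse event (AE) is considered treatment-emergent relative to the study intervention if the event start date is during the on-treatment period".
- Section 6.8.1: "All analyses will be based on treatment emergent adverse events (TEAE) unless otherwise specified". Events that are not treatment-emergent are only flagged in listings.

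**The concern.** Read together, these rules order the information the wrong way round. A site that knows nothing about the onset of an event that stopped after first dose has it counted as a TEAE. A site that knows the month, and that month is the month of first dose, has it dated before treatment and removed from the tables. The SAP offers no other route to TEAE status, such as worsening on treatment or a stop date after first dose.

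For early events the error runs one way: a post-dose event can be moved out of the tables, but an event that truly began before dosing is not moved in. Overall safety is a secondary objective. Protocol section 2.3.1 expects CRS mainly after the first doses, so the weeks just after first dose matter most. The error would also be hard to notice. AE collection starts at consent (protocol section 8.3.1), so an imputed pre-dose date looks like an ordinary screening event. The summaries of AEs of special interest and of other AEs of clinical interest (SAP sections 6.8.1.1 and 6.8.1.2) share the TEAE default and are exposed as well.

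**Working it through.** The documents state no figure on partial AE dates, so there is none to reproduce. The check has two steps.

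**1. Which rule applies.** AE onset is a start date used in a calculation: section 5.2.4 names it as an example in defining study day ("The study day for assessments occurring on or after the first dose of study intervention (eg, adverse event onset, disease measurement"), and section 3.5.1 uses it for treatment emergence. Sections 5.3.3.1 to 5.3.3.4 give no rule for a partial AE onset, so section 5.3.3.5 takes it.

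Worked cases, each with the onset day missing:

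| First dose | True onset | Imputed onset | TEAE? |
|---|---|---|---|
| 15 March 2022 | 20 March 2022 | 1 March 2022 | No |
| 15 March 2022 | 20 April 2022 | 1 April 2022 | Yes |
| 1 March 2022 | 20 March 2022 | 1 March 2022 | Yes |

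For first dose on 15 March with the onset entirely unknown, section 5.3.3.1 gives 15 March and a TEAE, provided first dose is earlier than the stop date.

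**2. How often this happens when the day is missing.** Two assumptions are not in the documents: first-dose dates are uniform over the calendar, and true onset is uniform over study days 1 to *w*.

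Take a month of *m* days, first dose on day *d*, and *w* no larger than *m*. The event is lost if *d* is at least 2 and the onset is still in that month, which holds for min(*w*, *m* − *d* + 1) of the *w* onset days. Summing over *d* = 2 to *m* gives *w*(*m* − *w*) + *w*(*w* − 1)/2. Dividing by *wm* gives:

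share lost = 1 − (*w* + 1)/(2*m*)

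Over a four-year calendar (48 months, 1,461 days), weighting each first-dose date equally:

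share lost = 1 − 48(*w* + 1)/(2 × 1,461)

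If only the year is known, 4 year-starts replace the 48 month-starts:

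share lost = 1 − 4(*w* + 1)/(2 × 1,461)

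| True onset within study days | Day missing | Only year known |
|---|---|---|
| 1–2 | 1 − 144/2,922 = 95.1% | 1 − 12/2,922 = 99.6% |
| 1–7 | 1 − 384/2,922 = 86.9% | 1 − 32/2,922 = 98.9% |
| 1–14 | 1 − 720/2,922 = 75.4% | 1 − 60/2,922 = 97.9% |
| 1–28 | 1 − 1,392/2,922 = 52.4% | 1 − 116/2,922 = 96.0% |

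Enumerating every first-dose date in a 1,461-day span gives the same values for 2, 7 and 28 days. The weighting of month lengths matters little: one month each of 28, 30 and 31 days (89 days) gives 1 − 3(*w* + 1)/178, which is 86.5%, 74.7% and 51.1% for 7, 14 and 28 days.

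For a day-missing event in the month of first dose, the imputed date precedes dosing for every first-dose date except the 1st: 1,413/1,461 = 96.7%. With the onset set to first dose in that situation, the share lost is 0% in every row.

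**The case against.** The SAP never says in words that partial AE onsets go to section 5.3.3.5. AE dates have their own section, and the default in section 5.3 is no imputation unless specified, so one could argue that no rule exists. That reading strains the words of the catch-all, which covers partial dates not dealt with elsewhere. It would also leave treatment emergence undecidable for these records, so the same sentence would still be needed.

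The stronger objection concerns impact, and most of it stands. Participants are inpatients around C1D1 and C1D4 with vital signs at least every 4 hours, Cycle 1 visits are frequent, and CRS and ICANS symptoms have dedicated CRF pages. The prominent early toxicities are therefore the least likely to lack a day; vague, low-grade or outpatient events are likelier. The percentages are conditional on a missing day and do not measure the effect on any reported rate. The primary endpoint has no imputation (SAP section 6.1), the DLT window starts at the first 116 or 152 mg dose, the enrollment-hold rules are not stated in terms of TEAEs, and death and laboratory summaries do not depend on AE onset. Affected events stay visible in listings.

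Two further points are fair. At the other end of the on-treatment window, the first-of-month rule can pull a late event back inside and add a TEAE, so the one-way direction applies to early events only. And some day-missing events in the month of first dose will truly be pre-dose.

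**Conclusion.** The concern holds. This is a stated rule that gives a wrong classification and contradicts the SAP's own conservative treatment of fully missing onsets. Unless first dose fell on the 1st, every truly post-dose AE with a missing day in the month of first dose is classed as pre-treatment. Under the uniform-date assumptions that is about 87% of day-missing events with onset on study days 1 to 7 and about 52% over days 1 to 28. Year-only onsets in the calendar year of first dose fare worse, at 96% or more.

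The absolute effect cannot be derived, because the documents do not give the number of partial AE dates; it is probably small. The consequence is confined to descriptive TEAE-based tables, including those for AEs of special and of clinical interest. The change should be made, but it does not bear on the primary result.

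**What to change.** Add to SAP section 5.3.3.1 a rule for partial AE onset dates. If the known part (month and year, or year alone) matches that of first dose, impute the date of first dose unless the AE stop date is earlier. In all other cases use the first day of the known month or year. State in section 5.3.3.5 that AE onset is excluded from its scope.

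The cost is one or two sentences in the SAP and one programming rule. Some events that truly began before dosing may be counted as TEAEs, which is the direction the SAP already accepts for wholly missing onsets. The check against the stop date removes those known to have ended before treatment.
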